16. Participants (except those in Phase II Group 5) have not recovered from all toxicities related to prior anticancer therapies to grade  $\leq 1$  (CTCAE v 4.03). Participants in Phase II Group 5 will use version 5.0. Participants with any grade of alopecia are allowed to enter the study.
17. **Participants in Phase Ib and Phase II Groups 1 to 4** have out of range laboratory values defined as:
  - Absolute Neutrophil Count (ANC)  $< 1.5 \times 10^9/L$  ( $1.5 \times 10^3/\mu L$ )
  - Hemoglobin (Hgb)  $< 9$  g/dL (90 g/L)
  - Platelets (PLT)  $< 75 \times 10^9/L$  ( $75 \times 10^3/\mu L$ )
  - Total bilirubin  $> 1.5$  x upper limit of normal (ULN)
  - AST and/or ALT  $> 3$  x ULN, except for participants with liver metastasis who may not be included if AST and/or ALT  $> 5$  x ULN
  - Alkaline phosphatase (ALP)  $> 5$  xULN
  - Calculated creatinine clearance  $< 45$  mL/min (0.75 mL/sec) using Cockcroft-Gault formula
  - Asymptomatic serum amylase or lipase  $>$  Grade 2
  - Serum amylase or serum lipase CTCAE grade  $\geq 1$  with signs and/or symptoms suggesting pancreatitis or pancreatic injury (e.g. elevated P-amylase, abnormal imaging findings of pancreas, etc.)

Participants in Phase II Group 5 have out of range laboratory values defined as:

- Absolute Neutrophil Count (ANC)  $< 1.5 \times 10^9/L$  ( $1.5 \times 10^3/\mu L$ ) without growth factor support
- Hemoglobin (Hgb)  $< 9$  g/dL (90 g/L)
- Platelets (PLT)  $< 100 \times 10^9/L$  ( $100 \times 10^3/\mu L$ )
- Total bilirubin  $> 1.5$  x upper limit of normal (ULN)
- AST and/or ALT  $> 2.5$  x ULN except for participants with liver metastasis, who may not be included if AST and/or ALT  $> 5$  x ULN
- Alkaline phosphatase (ALP)  $> 5$  xULN

- Calculated creatinine clearance (using Cockcroft-Gault formula) < 50 mL/min
  - Asymptomatic serum amylase increase grade 1 and 2 are allowed if at the beginning of the study is confirmed to have no signs and/or symptoms suggesting pancreatitis or pancreatic injury (e.g., elevated P-amylase, abnormal imaging findings of pancreas, etc.)
  - Serum lipase > ULN
18. Participants have the following laboratory values outside of the laboratory normal limits or cannot be corrected to within normal limits with supplements during screening:
- Potassium
  - Magnesium
  - Phosphorus
  - Total calcium (corrected for serum albumin)
19. Participants receiving treatment with medications that are known to be:
- strong inhibitors or inducers of CYP3A4/5,

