## 6.3 Dose modifications for toxicities

### 6.3.1 Dose modification and dose interruption

For participants who do not tolerate the protocol-specified dosing schedule due to drug related toxicities, dose interruptions and/or reductions are recommended in order to allow participants to continue the study treatment. For the dose escalation part of the study, dose reductions during cycle 1 are only allowed if a DLT is observed and recorded.

Table 6-7 provides recommendations for dose modification and dose interruption (i.e., interruption and re-initiation criteria for nazartinib and capmatinib treatment).

Refer to Table 6-5 and Table 6-6 for recommended dose reduction steps for the Phase II part of the study.

If, due to study drug related toxicity, a participant requires a dose interruption of >21 days from the intended day of the next scheduled dose, then the participant must be discontinued from the study treatment unless described otherwise.

Each participant is only allowed two dose reductions on each drug. In addition, a participant must discontinue treatment with nazartinib and capmatinib if, after treatment is resumed at a lower dose, the toxicity recurs with the same or worse severity.

Exceptions on dose interruptions and modifications can be made on a case by case basis after discussion with Novartis and Investigator.

In exceptional cases, after discussion with Novartis, participants may be allowed to continue treatment or resume treatment with only one of the investigational drugs.

All dose interruptions or modifications must be recorded on the Dosage Administration Record CRF.

In case of study treatment interruption, visit schedule should still be followed and assessments performed as per Table 7-1 and Table 7-2.

After dose modification, re-escalation to a previous dose level is not permitted apart from the exceptional cases described in Table 6-14 and Table 6-15.

Events not included in the study protocol or the reference guidance documents should be managed according to local practices.

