Grade 3 (> 5.0 - 20.0 × ULN)	
Omit study treatment. Monitor LFTsc weekly, or more frequently if clinically indicated until resolved to ≤ grade 1, then resume nazartinib at the same dose level:
 
 
• If resolved in ≤ 7 days, then resume capmatinib at same dose level
 
• If resolved in > 7 days, then resume capmatinib at ↓ 1 dose level
 
• If recurrence during nazartinib monotherapy, omit study treatment until resolved to ≤ grade 1, then resume nazartinib at ↓ 1 dose level
 
• If no recurrence after 7 days of nazartinib monotherapy at ↓ 1 dose level, then resume capmatinib at ↓ 1 dose level
 

Grade 4 (> 20.0 × ULN)	Mandatory: Permanently discontinue both study drugs.

Worst toxicity CTCAE a Grade (value)	Recommendation
	Repeat LFTs c as soon as possible, preferably within 48-72 hours from awareness of the abnormal results; monitor LFTs c weekly, or more frequently if clinically indicated, until resolved to baseline or stabilization over 4 weeks.
Combinedd elevations of AST or ALT and concurrent Total bilirubinf	

For participants with normal baseline ALT and AST and total bilirubin value: AST or ALT > 3.0 × ULN combined with total bilirubin > 2.0 × ULN without evidence of cholestasise
 
or
 
For participants with elevated baseline AST or ALT or total bilirubin value: [AST or ALT > 3x baseline or [AST or ALT > 8.0 × ULN], whichever is lower, combined with [total bilirubin >2x baseline AND >2.0 × ULN]
	
Permanently discontinue nazartinib and capmatinib in the absence of signs of cholestasis, hemolysis, and if alternative causes of the liver injury have been excluded (e.g., concomitant use of hepatotoxic drug(s), alcoholic hepatitis, viral hepatitis etc.) Repeat LFTsc as soon as possible, preferably within 48 hours from awareness of the abnormal results, then with weekly monitoring of LFTsb, or more frequently if clinically indicated, until AST, ALT, or bilirubin have resolved to baseline or stabilized over 4 weeks.

METABOLICh	
Amylase and/or lipase elevation	

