Grade 3 (>2.0 - 5.0 x ULN with signs or symptoms; >5.0 x ULN and asymptomatic)	
Omit study treatment until resolved to ≤ grade 1, then resume nazartinib at the same dose level:
 
 
• If resolved in ≤ 14 days, resume capmatinib at the same dose level
 
• If resolved in > 14 days, resume capmatinib at ↓ 1 dose level
 
• If recurrence of grade 3 toxicity during nazartinib monotherapy, omit study treatment until resolved to ≤ grade 2, then ↓ 1 dose level nazartinib
 
• If no recurrence of grade 3 toxicity after 7 days of nazartinib monotherapy at ↓ 1 dose level, resume capmatinib at ↓ 1 dose level
 

Grade 4 (>5.0 x ULN and with signs or symptoms)	Permanently discontinue capmatinib and omit nazartinib until resolved to grade ≤ 2, then maintain dose level of nazartinib. Monitor for recurrence of grade 3 toxicity after 7 days or sooner if clinically indicated

Note: Perform diagnostic procedures (e.g., abdominal CT scan or ultrasound) to exclude pancreatic pathology. Withhold study treatment for acute onset of new or progressive unexplained abdominal symptoms, such as severe pain or vomiting; if diagnosed with pancreatitis ≥ grade 3 permanently discontinue from capmatinib treatment.
	
HBV and HCV reactivation	
Refer to Table 6-10 , Table 6-11 and Table 6-12 , and Section 6.3.2 for details.	
CARDIAC	
Electrocardiogram QT corrected (QTc) interval prolonged	
Grade 3 (QTc ≥ 501 ms on at least two separate ECGs)	
Omit study treatment until resolved to ≤ grade 1 then:
 
 
• If resolved in ≤ 7 days, resume capmatinib at same dose level and nazartinib at ↓ 1 dose level
 
• If resolved in > 7 days, resume capmatinib and nazartinib at ↓ 1 dose level
 

Grade 4 ([QT/QTc ≥ 501 or > 60 ms change	Permanently discontinue nazartinib and capmatinib.

Worst toxicity CTCAEa Grade (value)	Recommendation
from baseline] and [Torsades de pointes or polymorphic ventricular tachycardia, or signs/symptoms of serious arrhythmia])	Obtain local cardiologist (or qualified specialist) consultation and repeat cardiac monitoring as indicated until the QTcF returns to <481 ms.
VASCULAR DISORDERS	

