Grade 3 (> 3.0 - 10.0 x ULN)	Omit dose until resolved to ≤ grade 1, then 
 
• If fully resolved in ≤ 7 days, resume at ↓ 1 dose level
 
• If fully resolved in > 7 days, permanently discontinue capmatinib treatment
 

Grade 4 (> 10.0 x ULN)	Mandatory: Permanently discontinue capmatinib treatment
Isolated AST or ALT elevation	
Grade 1 (> ULN - 3 x ULN)	Maintain dose level
Grade 2 (> 3.0 - 5.0 x ULN)	Maintain dose level
Grade 3 (> 5.0 - 20.0 x ULN)	Omit dose until resolved to ≤ grade 1 (or ≤ grade 2 if grade 2 elevation at baseline) then 
 
• If fully resolved in ≤ 7 days, then resume at the same dose level
 
• If fully resolved in > 7 days, resume at ↓ 1 dose level
 

Grade 4 (> 20.0 x ULN)	Mandatory: Permanently discontinue capmatinib treatment
Combined elevations of AST or ALT and Total Bilirubinb,c,d	
For participants with normal baseline ALT and AST and total bilirubin value: AST or ALT > 3.0 x ULN combined with total bilirubin > 2.0 x ULN without evidence of cholestasis or hemolysis OR For participants with elevated baseline AST or ALT or total bilirubin value:	Mandatory: Permanently discontinue capmatinib treatment

Worst toxicity CTCAE Gradea during a cycle of therapy	Recommendation
[AST or ALT > 3 x baseline] OR [AST or ALT > 8.0 x ULN], whichever is lower, combined with [total bilirubin > 2 x baseline AND > 2.0 x ULN] without evidence of cholestasis or hemolysis	
METABOLIC	
Amylase and/or lipase elevation	
Grade 1 (> ULN - 1.5 x ULN)	Maintain dose level
Grade 2 (> 1.5 - 2.0 x ULN; > 2.0 - 5.0 x ULN and asymptomatic)	Maintain dose level
Grade 3 (> 2.0 - 5.0 x ULN with signs or symptoms; > 5.0 x ULN and asymptomatic)	Omit the dose until resolved to ≤ grade 1, then 
 
• If fully resolved in ≤ 14 days, resume at the same dose level
 
• If fully resolved in > 14 days, then resume at ↓ 1 dose level
 

Grade 4 (> 5.0 x ULN with signs or symptoms)	Permanently discontinue capmatinib treatment
CARDIAC	
Electrocardiogram QT corrected (QTc) interval prolonged	
Grade 1 (QTcF 450-480 ms) Grade 2 (QTcF 481-500 ms)	Maintain dose level

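### For Group 5, three Grade 3 restart rules (AST/ALT in Table 6-7, amylase in Tables 6-7 and 6-8) make no allowance for the elevated baselines that criterion 17 admits, and conflict with neighbouring rules

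*Protocol*

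**What the plan says.** **Entry.** In Section 5.3, criterion 17, the Group 5 list excludes participants with liver metastases only when AST and/or ALT exceeds 5 x ULN. For amylase it says "Asymptomatic serum amylase increase grade 1 and 2 are allowed if at the beginning of the study" there are no signs or symptoms of pancreatic injury. Lipase above ULN is excluded.

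**Restart after a first Grade 3 event.**
- Table 6-7 (combination), isolated AST/ALT: treatment is withheld and liver tests are monitored weekly, "or more frequently if clinically indicated until resolved to ≤ grade 1, then resume nazartinib at the same dose level".
- Table 6-7, amylase and/or lipase: "Omit study treatment until resolved to ≤ grade 1, then resume nazartinib at the same dose level".
- Table 6-8 (capmatinib monotherapy), amylase and/or lipase: "Omit the dose until resolved to ≤ grade 1, then" the dose depends on time to recovery.
- Table 6-8, isolated AST/ALT, is different: "Omit dose until resolved to ≤ grade 1 (or ≤ grade 2 if grade 2 elevation at baseline) then" the dose depends on time to recovery.

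**Length of interruption.** Section 6.3.1 limits interruptions that the study drugs themselves cause: once "a participant requires a dose interruption of >21 days from the intended day of the next scheduled dose, then the participant must be discontinued", which here means stopping study treatment. The sentence goes on to except whatever the protocol describes otherwise. The section also permits case-by-case exceptions after discussion between the sponsor and the investigator.

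**Order of treatments.** Under Sections 6.1.1 and 6.1.2, Group 5 starts on capmatinib alone (Table 6-8). The combination (Table 6-7) is an option after radiological progression.

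**The concern.** Criterion 17 accepts a Grade 2 value at entry, while three restart rows treat Grade 1 as the recovered state. For a participant admitted at Grade 2, coming back to the admitted level does not meet the restart condition. Recovery then means falling below the level at which the protocol judged the participant fit to start.

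Two things are at stake. For amylase, the rule can act during capmatinib monotherapy. It could shorten exposure while the primary ORR is being measured and add non-progression discontinuations to the monotherapy DOR, PFS and tolerability data. For AST/ALT, it acts only in the combination extension, where tolerability is a secondary objective in Table 3-1. There, a participant covered by the baseline clause of Table 6-8 on monotherapy moves to a table without one.

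**Working it through.** No stated figure has to be reproduced. The check sets the entry limits beside the restart rows, taking grades as the tables print them in multiples of ULN.

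**Printed grades.** AST/ALT: Grade 1 is up to 3 x ULN and Grade 2 is above 3 to 5 x ULN (Tables 6-7 and 6-8). Amylase in Table 6-8: Grade 1 is up to 1.5 x ULN; Grade 2 is above 1.5 to 2.0 x ULN, or above 2.0 to 5.0 x ULN if asymptomatic. Criterion 17 can therefore admit AST/ALT above 3 to 5 x ULN and, on Table 6-8's bands, asymptomatic amylase up to 5 x ULN.

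**Restart level after a first Grade 3 event.**

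| Table | Isolated AST/ALT | Amylase |
|---|---|---|
| 6-8, capmatinib alone | Grade 1, or Grade 2 if Grade 2 at baseline | Grade 1, no baseline clause |
| 6-7, combination | Grade 1, no baseline clause | Grade 1, no baseline clause |
| 6-9, nazartinib alone | Rows set by baseline; for above 10 to 20 x ULN, Grade 1 or baseline | Grade 2 |

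Of the four cells for Group 5's planned treatments (Tables 6-8 and 6-7), three have no baseline allowance. The exception is AST/ALT on monotherapy.

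**Signs that the strict level is not applied consistently.**
- Table 6-7 amylase: a first Grade 3 needs Grade 1, but a Grade 3 recurrence on nazartinib alone needs only Grade 2. After Grade 4, when capmatinib is stopped, nazartinib resumes at Grade 2. The milder first event carries the stricter condition.
- Table 6-7 refers to baseline elsewhere: in the Grade 2 creatinine row and in the combined AST/ALT and bilirubin row.
- Dosing at Grade 2 is otherwise accepted: dose is maintained for Grade 2 AST/ALT (Tables 6-7 and 6-8) and for Grade 2 amylase (Table 6-8).
- Footnote h to Table 6-7 requires permanent discontinuation if asymptomatic Grade 2 amylase or lipase occurs again at the reduced dose. For someone admitted at Grade 2, it could be read as triggered by their own baseline.

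**Illustrations (baselines assumed, not taken from the protocol).**
- AST/ALT baseline 4 x ULN. The hold begins above 5 x ULN: 5.0/4.0 = 1.25, a 25% rise. Table 6-7 restarts at 3 x ULN: 3.0/4.0 = 0.75, 25% below baseline. At 6 x ULN the tables give three answers: 6-7 withholds both drugs until 3 x ULN, 6-8 withholds capmatinib until 5 x ULN, and 6-9 maintains the dose.
- Amylase baseline 3 x ULN, asymptomatic. Grade 3 begins above 5 x ULN: 5.0/3.0 = 1.67, a 67% rise. Restart at 1.5 x ULN: 1.5/3.0 = 0.50, half of baseline.

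**A limit on the amylase comparison.** Table 6-9 prints Grade 2 amylase as ending at 2.0 x ULN and Grade 3 as above 2.0 to 5.0 x ULN even without symptoms, although it cites the same CTCAE version as Table 6-8. Its Grade 2 restart is looser than Grade 1 but would not cover a baseline of 3 x ULN.

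**The case against.** A reader might infer that the dose tables never let a Group 5 participant restart above Grade 1, so that one transient Grade 3 value cannot recover and ends treatment. The protocol does not support that. Table 6-8 provides for a Grade 2 AST/ALT baseline, and it governs the period in which the primary ORR is measured. Values may fall below the entry level. The 21-day rule covers only drug-related interruptions, leaves room for other provisions, and sits beside a case-by-case exception. Section 6.3.1 also presents Table 6-7 as recommendations.

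It can also be said that entry and restart limits serve different purposes, that two drugs together may warrant a stricter restart than one, and that Tables 6-7 and 6-8 agree on a first Grade 3 amylase event. The amylase case is narrow: lipase above ULN is excluded at entry, and raised amylase is admitted only without signs of pancreatic injury. Participants who stop for reasons other than progression are still followed for progression (Section 4.1). Section 2.1 cites a 6-week median time to response from another capmatinib study, so a later stop need not change best response.

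These points limit the consequence but leave the inconsistency. Deliberate strictness does not explain why Table 6-7 asks less after a recurrent Grade 3 or a Grade 4 amylase event than after a first Grade 3, or why three tables handle the same AST/ALT baseline in three ways. The exception clause sets no criterion, so similar participants may be handled differently.

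**Conclusion.** The concern holds in this limited form. In three rows the restart condition can lie below a level that criterion 17 admits, and those rows conflict with neighbouring rules. A participant back at the admitted level may be barred from restarting. They may then be discontinued if the interruption is drug related, exceeds 21 days and no exception is granted.

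Only the amylase rows in Tables 6-7 and 6-8 and the AST/ALT row in Table 6-7 are affected, and only the Table 6-8 amylase row can act during monotherapy. With about 30 participants, one changed best response moves the ORR by 1/30 = 3.3 percentage points. That figure applies to amylase alone, and only if the stop changed the response. The AST/ALT row bears on the extension and its tolerability data, so it has no price in ORR points.

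Few participants are likely to be affected. The protocol gives no prevalence of elevated baselines or rate of Grade 3 events, so no count is offered. Groups 1 to 4 had similar entry limits, but the Amendment 07 rationale says none of them remains on treatment. Section 6.3.4.2 and Table 6-16 were not available for this check, so a relevant exception there cannot be ruled out.

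**What to change.** Reconcile criterion 17 with the isolated AST/ALT row of Table 6-7 and the amylase rows of Tables 6-7 and 6-8, including footnote h, so that participants admitted with an elevated baseline are handled consistently across the tables. Put the printed amylase grades of Tables 6-8 and 6-9 on one scale at the same time. State in Section 6.3.1 how the 21-day rule applies to these participants. The sponsor's clinical and safety leads decide the restart level; none is proposed here.

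The cost is small: footnotes or row edits and one sentence in the next amendment, with no added visits or tests.

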Grade 2 (> 1.5 and ≤ 3.0 × ULN)	Omit study treatment. Monitor LFTs c weekly, or more frequently if clinically indicated until resolved to ≤ grade 1, then resume nazartinib and capmatinib at the same dose level.
Grade 3 (> 3.0 and ≤ 10.0 × ULN) g	
Omit study treatment. Monitor LFTsc weekly, or more frequently if clinically indicated until resolved to ≤ grade 1, then resume nazartinib at the same dose level.
 
 
• If no recurrence of grade 3 toxicity after 7 days of nazartinib monotherapy, resume capmatinib at ↓ 1 dose level
 
• If recurrence of grade 3 toxicity on maintained dose level of nazartinib and ↓ 1 dose level of capmatinib, omit study treatment until resolved to ≤ grade 1, then resume nazartinib at same dose level and Capmatinib ↓ 1 dose level
 
• If recurrence of grade 3 toxicity during nazartinib monotherapy, omit study treatment until resolved to ≤ grade 1, then resume nazartinib at ↓ 1 dose level
 
• If no recurrence of grade 3 toxicity after 7 days of nazartinib monotherapy at ↓ 1 dose level, resume capmatinib at ↓ 1 dose level
 

Grade 4 (> 10.0 × ULN) g	
Discontinue participant permanently from capmatinib and nazartinib.
 
The participant should be monitored weekly (including LFTsc), or more frequently if clinically indicated, until total bilirubin has resolved to baseline or stabilization over 4 weeks.

Isolated AST or ALT elevation	
Grade 2 (> 3.0 and ≤ 5.0 × ULN)	
Maintain dose level of both drugs with LFTsc monitored per protocol.
 
Repeat LFTsc as soon as possible, preferably within 48-72 hours from awareness of the abnormal results; if abnormal lab values are confirmed upon the repeat test, then monitor LFTsc weekly, or more frequently if clinically indicated, until resolved to ≤ grade 1.

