
All dose modifications should be based on the worst preceding toxicity.
 
a Common Terminology Criteria for Adverse Events (CTCAE) version 5.0
 
b If grade 3 or 4 hyper-bilirubinemia is due to the indirect (non-conjugated) component only, and hemolysis as the etiology has been ruled out as per institutional guidelines (e.g., Review of peripheral blood smear and haptoglobin determination), then ↓ 1 dose level and continue treatment at the discretion of the investigator.
 
c LFTs include albumin, ALT, AST, total bilirubin (fractionated if total bilirubin > 2.0 × ULN), alkaline phosphatase (fractionated if alkaline phosphatase > 2.0 × ULN) and gamma-glutamyl transpeptidase (GGT). For isolated elevations of any grade of alkaline phosphatase and/or GGT, maintain dose level.
 
d “Combined” defined as: total bilirubin increases to the defined threshold concurrently with ALT/AST increase to the defined threshold
 
e “Cholestasis” defined as: ALP elevation (> 2 × ULN and R value < 2) in participants without bone metastasis, or elevation of ALP liver fraction in participants with bone metastasis Note: The R value is calculated by dividing the ALT by the ALP, using multiples of the ULN for both values. It denotes the relative pattern of ALT and/or ALP elevation is due to cholestatic or hepatocellular liver injury
 
f If combined elevations of AST or ALT and total bilirubin do not meet the defined thresholds, please follow the instructions for isolated elevation of total bilirubin and isolated elevation of AST/ALT, and take a conservative action based on the degree of the elevations (e.g. discontinue treatment at the situation when omit dose is needed for one parameter and discontinue treatment is required for another parameter). After all elevations resolve to the defined thresholds that allow treatment re-initiation, re-start the treatment either at the same dose or at one dose lower if meeting a criterion for dose reduction
	

Worst toxicity CTCAE a Grade (value)	Recommendation

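### In Table 6-7 the row for combined AST/ALT and bilirubin elevation makes the permanent stop depend on excluding other causes and states no dosing hold, whereas Tables 6-8 and 6-9 make the stop mandatory at the same normal-baseline trigger

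*Protocol*

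**What the plan says.** Section 6.3.1 gives three dose-modification tables: Table 6-7 for the combination, Table 6-8 for capmatinib alone and Table 6-9 for nazartinib alone. Each has a row for combined elevation of AST or ALT and total bilirubin.

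- **Table 6-7, both drugs.** With normal baseline values, the row applies at AST or ALT above 3.0x ULN with total bilirubin above 2.0x ULN and no evidence of cholestasis. The action is "Permanently discontinue nazartinib and capmatinib in the absence of signs of cholestasis, hemolysis, and if alternative causes of the liver injury have been excluded". Concomitant hepatotoxic drugs, alcoholic hepatitis and viral hepatitis are given as examples of other causes. The remainder of the cell covers repeat liver tests, preferably within 48 hours, and then weekly monitoring.
- **Table 6-8, capmatinib alone.** The normal-baseline trigger is "AST or ALT > 3.0 x ULN combined with total bilirubin > 2.0 x ULN without evidence of cholestasis or hemolysis" and the action is "Mandatory: Permanently discontinue capmatinib treatment".
- **Table 6-9, nazartinib alone.** The numeric thresholds are the same, cholestasis is the only carve-out, and permanent discontinuation is again labelled mandatory.

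Elsewhere in Table 6-7, isolated bilirubin grades 2 and 3 and isolated AST/ALT grade 3 begin "Omit study treatment. Monitor LFTs". Isolated AST/ALT grade 2 reads "Maintain dose level of both drugs with LFTs" being monitored. Isolated AST/ALT grade 4 reads "Mandatory: Permanently discontinue both study drugs". Footnote f says: "If combined elevations of AST or ALT and total bilirubin do not meet the defined thresholds, please follow the instructions for isolated elevation". It adds that the conservative action should be taken.

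**The concern.** Excluding the listed causes takes investigation. Until that is done, the condition for the permanent stop is not met, and the row gives no other dosing instruction. It is also silent on dosing if another cause is found. The neighboring rows that do contain a hold are headed as isolated elevations, and footnote f sends a reader to them only when the combined threshold is not reached.

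This is the most serious liver picture in the table, and it arises with two drugs on board. A Group 5 participant starts on capmatinib alone under Table 6-8 and may add nazartinib at progression, which brings Table 6-7 into force. The same laboratory result then moves from a mandatory stop to a conditional one because a second drug was added. The text available gives no reason for that. The amendment history records that hepatotoxicity criteria were once modified because of a Hy's law case in another capmatinib study, so the risk is a known one.

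**Working it through.** No sample size, power or error rate is involved. The check is a comparison of rows. All cases assume normal baseline values and no cholestasis or hemolysis, because the elevated-baseline triggers differ between the tables and cannot be compared directly.

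**Within Table 6-7** (values in multiples of ULN):

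| Case | ALT | Bilirubin | Threshold check | Dosing instruction in the applicable row |
|---|---|---|---|---|
| 1 | 4 | normal | 3.0 < 4 ≤ 5.0: isolated AST/ALT grade 2 | maintain both |
| 2 | 6 | normal | 5.0 < 6 ≤ 20.0: isolated AST/ALT grade 3 | omit |
| 3 | normal | 2.5 | 1.5 < 2.5 ≤ 3.0: isolated bilirubin grade 2 | omit |
| 4 | 4 | 1.8 | 4 > 3.0 but 1.8 ≤ 2.0: combined threshold not met. Footnote f applies, and since 1.8 > 1.5 the bilirubin grade 2 row is the more conservative | omit |
| 5 | 4 | 2.5 | 4 > 3.0 and 2.5 > 2.0: combined row | permanent stop if other causes are excluded; no hold stated |
| 6 | 25 | normal | 25 > 20.0: isolated AST/ALT grade 4 | mandatory permanent stop of both |

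The informative pair is 4 and 5. ALT stays at 4x while bilirubin rises from 1.8x to 2.5x, and the written instruction goes from an explicit hold to none. Case 6 shows that the same table can require a stop with no alternative-cause condition. The cases were chosen to show where the rows change. They are not a sample, and the documents give no rate for such events in the combination stage.

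**Case 5 across the three tables:**

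| Table | Drugs | Carve-outs | Alternative-cause condition | Labelled mandatory |
|---|---|---|---|---|
| 6-7 | both | cholestasis, hemolysis | yes | no |
| 6-8 | capmatinib | cholestasis, hemolysis | no | yes |
| 6-9 | nazartinib | cholestasis | no | yes |

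Hemolysis appears in both Table 6-7 and Table 6-8, so it does not separate the combination from both single-drug tables. The alternative-cause condition and the missing mandatory label do.

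**A work-up hold elsewhere in Table 6-7.** The grade 1 pneumonitis/ILD row interrupts study treatment during the diagnostic work-up and then says when it may resume. The combined liver row has no equivalent.

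**The case against.** The strongest reply is that the row should not be read alone. Its condition turns on excluding other causes, and the protocol has dedicated text for that: Section 6.3.4.2 on potential drug-induced liver injury, Table 6-17 on ruling out alternative causes, and Tables 6-10 to 6-12 for hepatitis reactivation, to which Table 6-7 has its own referring row. None of these was available for this review, and an interruption may well be stated there. This stands, and it limits the claim to the row. It does not remove the mismatch with Tables 6-8 and 6-9.

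Second, the logic of the table points toward holding. At this trigger bilirubin is always above 2.0x ULN, a level at which the isolated bilirubin grade 2 and 3 rows omit treatment. The general note says "All dose modifications should be based on the worst preceding toxicity", and footnote f asks for caution even in milder pairs. A careful investigator would probably hold. A reader might infer from the row that dosing may continue during the work-up, but no text permits that. What is conditional is the permanent stop. The defect is that the interim hold is not written.

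Third, it is tempting to say that the single-drug tables order an immediate stop. Neither uses that word, and both still require a check for cholestasis, with hemolysis added in Table 6-8. Nor is every milder picture in Table 6-7 held, as case 1 shows.

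Fourth, the exception is defensible in itself. Participants positive for HBsAg or HBV-DNA may enroll, as may those with liver metastases and AST/ALT up to 5x ULN, so liver injury not caused by study drug is foreseeable. Section 6.3.1 is also framed around drug-related toxicity. That supports keeping an exception. It does not explain why the exception applies to two drugs and not to one, or why the interim is left unstated.

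**Conclusion.** The point holds at row level. As written, the Table 6-7 combined-elevation row gives a weaker dosing instruction than the sub-threshold pair in the same table, and a weaker one than either drug alone at the same normal-baseline trigger. Whether the whole protocol lacks a hold is not established, because the liver-injury follow-up section and the related tables were not seen.

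The practical reach is small. No participant from Phase Ib or Groups 1 to 4 remains on treatment, so exposure is limited to those among the approximately 30 planned Group 5 participants who enter the optional combination stage. No endpoint, interim rule or analysis is affected. It should still be corrected, because it concerns the safety of individual participants and the correction is short. Confidence is medium, for the reason given about the unseen text.

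**What to change.** Reword the action in the Table 6-7 combined-elevation row along these lines: *Mandatory: interrupt nazartinib and capmatinib once the combined threshold is met and throughout the work-up; permanently discontinue both unless cholestasis, hemolysis or another cause is established.*

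Then make the three tables agree. If the alternative-cause exception is kept, give this row its own restart rule, since the one in footnote f is written for sub-threshold cases, and state whether the exception also applies in Tables 6-8 and 6-9. If it is not kept, delete it from Table 6-7 and shorten the wording above to match. Check the result against Section 6.3.4.2, Table 6-17 and Tables 6-10 to 6-12.

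The cost is one rewritten row at the next amendment and, if the exception stays, a restart sentence and a line in each single-drug table. Some temporary interruptions will later prove unrelated to study drug. No procedures are added.
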